The intervention was rated as highly acceptable. Additionally, analyses revealed significant within-subjects decreases in past-month alcohol consumption, drinking days, and binge-drinking days post-intervention; however, there were no significant changes in past-month protective behavioral strategies and mindfulness practices. Although this pilot study provided critical feedback about intervention development and administration, it was intentionally small and did not include a control group, thereby limiting the interpretation of findings. The proposed study builds on this pilot work by replicating the study with a larger sample size, a community-based sample, and an assessment-only control group. Specific procedures are described below.

Chapter 2: Methods

Participants

Eighty participants will be recruited from Prolific, an online platform designed to screen and recruit potential research participants for online studies. Power analyses indicate that, with an N of 80 (two groups of 40), this study will be sufficiently powered to detect effect sizes of .20, an effect size consistent with other standalone, technology-delivered, cognitive behavioral interventions for alcohol use (Kiluk et al., 2019).

In order to be eligible for the study, participants must: (1) be a US resident, (2) be between the ages of 18 and 30; (3) report at least two binge-drinking episodes (i.e., four or more drinks in one sitting for cis women, five or more drinks in one sitting for cis men or transgender and

nonbinary individuals) per month over the past three months; (4) have an active Instagram page; and (5) report regular Instagram use (i.e., at least 2-3 times a week).

Participants will be randomized to either an intervention condition in which they will follow an Instagram page and engage with content during the six-week study period or to an assessment-only control condition in which they will be emailed assessment measures, but will not be exposed to intervention content.

Measures

Demographics will be assessed at baseline. Participants will be asked to answer questions about their sex, gender, age, race, ethnicity, sexual orientation, education level, and household income. State of residence will also be assessed.

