prioritize the things that matter to you and to achieve your goals! Put your values first, and the rest will follow”) or prompt participants to reflect on their own individual values and skills (e.g., “You did that! Give yourself credit where credit is due. Think about your goals and go for them!”).

Protective Behavioral Strategies. Protective behavioral strategy posts will reference specific behaviors that can increase or decrease the consequences of alcohol use (e.g., “Drinking games can be dangerous. Drinking too much, especially in short spans, can lead to alcohol poisoning. What was once fun can become frightening.”). Other posts will ask participants to reflect on protective behavioral strategies that they have used in the past or have seen others use effectively.

Procedure

Recruitment and Baseline. Eighty participants will be recruited using a screening survey administered through Prolific, a research recruitment website. Eligible participants will be given access to the main study on Prolific, and those randomized to the intervention condition will be invited to follow the study Instagram page. Before being given the Instagram page username, participants will be asked to agree to the following study guidelines/expectations:

- 1) They will follow the Instagram intervention page for the duration of the 6-week study
- 2) They will treat their fellow group members with respect and avoid “trolling” (i.e., contacting other participants, posting disrespectful comments, using obscene language, etc.)
- 3) They will participate, comment, and share when they feel comfortable doing so
- 4) They will ‘like’ intervention content posts as they appear on their feed (as a way of indicating that they have seen them)

5) While their comments and interactions on the page will not be seen by the general public, other participants will be able to view them and interact with them

After agreeing to these expectations, participants will be asked to provide their Instagram username, sent a baseline survey containing a link to the Instagram page and the baseline questionnaires, and instructed to begin following the Instagram page immediately.

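### After randomisation and before baseline, intervention participants must accept five expectations and give a username; controls have no such step, and nothing keeps refusers in the analysis

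*Combined protocol and SAP*

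**What the plan says.** The order of events is in Chapter 2: Methods, Procedure, Recruitment and Baseline. Candidates are screened on Prolific and eligible people get access to the main study. Then "those randomized to the intervention condition will be invited to follow the study Instagram page". The agreement step comes next: "Before being given the Instagram page username, participants will be asked to agree to the following study guidelines/expectations". Five expectations follow. The first is "They will follow the Instagram intervention page for the duration of the 6-week study"; others ask participants to like posts as they appear and to accept that other participants can see their comments. The text continues: "After agreeing to these expectations, participants will be asked to provide their Instagram username, sent a baseline survey containing a link to the Instagram page", together with the baseline questionnaires.

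Controls are described in the Participants section as an "assessment-only control condition in which they will be emailed assessment measures, but will not be exposed to intervention content". No agreement or username step is given for them.

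The Instagram-related eligibility criteria, also under Participants, are "4) have an active Instagram page; and (5) report regular Instagram use". Willingness to accept the expectations is not among the five criteria.

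Analytic Strategy and Hypotheses plans mixed repeated-measures ANOVAs on baseline and 10-week data, with transformation, multiple imputation and list-wise deletion as needed. It defines no analysis population and no intention-to-treat rule.

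**The concern.** Randomisation makes the arms comparable at the moment of allocation. A step that comes after allocation, applies to one arm and stands before the baseline survey can undo this. If some people decline, the intervention arm that is analysed contains only agreers, while the control arm contains people who would have agreed and people who would have declined.

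The protocol's own background makes refusal plausible. In the section on alcohol use disorder treatment it reports that 97.5% of emerging adults meeting criteria for a substance use disorder did not want treatment or feel they needed it. In the section on brief-intervention dissemination it says many heavy drinkers will not give even limited time to a computerised programme. Declining six weeks of following and liking posts may go with low readiness to cut down. If so, part of any larger fall in drinking in the intervention arm would be selection rather than effect. The planned analysis could not repair this, because a person without a baseline gives the model almost nothing to work from.

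**Working it through.** **1. Which arm the step applies to.** The text says 'participants' without naming an arm. The content settles it: the expectations concern following and liking the study page, and the survey that follows carries the link to it. Controls are not to see that content.

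**2. What happens to a refuser.** The baseline survey is sent after agreement, and no other route to it is described. The 10-Week Follow-Up Survey section says participants are emailed the survey and does not make this conditional on following the page. Read generously, a refuser could therefore have a 10-week measurement but no baseline. The ANOVA uses both time points. List-wise deletion removes such a person; imputation would have to construct the baseline from little or nothing.

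**3. The bias.** Let r be the share of the intervention arm that refuses, and m_A and m_R the mean changes that agreers and refusers would show. The full arm's mean is (1 - r)m_A + r·m_R. Analysing agreers only gives m_A. The error is

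m_A - [(1 - r)m_A + r·m_R] = r(m_A - m_R) = r × g.

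The documents give neither r nor g. Both are assumptions here, with g in SDs of change:

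| r | refusers of 40 | g = 0.1 | g = 0.5 |
|---|---|---|---|
| 10% | 4 | 0.01 SD | 0.05 SD |
| 20% | 8 | 0.02 SD | 0.10 SD |

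If g = 0 there is no bias. If refusers would have changed more than agreers, the sign reverses.

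**4. Against the target effect.** The plan states that "with an N of 80 (two groups of 40), this study will be sufficiently powered to detect effect sizes of .20", without naming the metric, alpha or power. Taking alpha as .05 two-sided:

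- As a standardised mean difference of .20 with 40 per arm, power is 14%.
- As Cohen's f for the group-by-time interaction, power is 71%, 85%, 94% and 99% at baseline-to-follow-up correlations of 0, .3, .5 and .7.

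The stated figure therefore cannot be reproduced uniquely, and the metric matters for the comparison:

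- Standardised mean difference .20, in the same SD units as the bias: 0.01/.20 = 5% to 0.10/.20 = 50%.
- Cohen's f on the two-group convention, d = 2 × .20 = .40: 0.01/.40 = 2.5% to 0.10/.40 = 25%.

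**5. False-positive rate.** With no true effect, change SD 1 and a two-sided 5% test (normal approximation):

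- r = 10%, g = 0.5: SE = √(1/36 + 1/40) = 0.230; bias/SE = 0.05/0.230 = 0.22; error rate 5.5%.
- r = 20%, g = 0.5: SE = √(1/32 + 1/40) = 0.237; bias/SE = 0.10/0.237 = 0.42; error rate 7.1%.

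**The case against.** The strongest reply is that the documents never say refusers are withdrawn, replaced or denied surveys. That is correct. A reader might infer that the plan excludes them; the text supports only the weaker statement that it gives them no route to a baseline and has no rule that retains them.

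The order can also be questioned. The paragraph on data collection waves speaks of avoiding delay between completing the baseline survey and starting the intervention, which could suggest that baseline comes first. It does not say that baseline precedes randomisation, and it does not displace the explicit order given just before it. The consent pages are not in the text reviewed, so what all candidates accepted beforehand cannot be seen.

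It is also fair to say that moving the agreement step is not the only remedy. If baseline were in hand for everyone and every randomised person were surveyed and analysed as randomised, declining the page would be non-adherence and the bias would vanish.

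Two further inferences are tempting and are not supported:

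- That giving a username makes intervention participants under-report drinking. As written, the username precedes both surveys, so a constant shift would cancel in the baseline-to-10-week comparison. Nothing says answers are linked to usernames.
- That the username request removes people without an active account from one arm only. An active page is an entry criterion for both arms, and the request is not described as an account check.

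**Conclusion.** The point stands as a flaw in the procedure as written: a step after randomisation, described for one arm only, precedes baseline measurement, and nothing retains those who refuse it. The arms can then no longer be assumed comparable. A reader might go further and conclude that they are not comparable, or that the trial is biased in favour of the intervention. The documents do not establish this, because they give neither the refusal rate nor how refusers would differ. Selection on readiness to change is plausible; refusal on privacy grounds need not follow it.

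The illustrative size, 0.01-0.10 SD, rests on assumed refusal of 10-20% and an assumed difference of 0.1-0.5 SD. The share of 5-50% of the target holds only if .20 is a standardised mean difference. At the upper difference of 0.5 SD the inflation of the false-positive rate is modest, but the step is easily moved and it touches the trial's central comparison.

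**What to change.** At the end of screening, show every candidate the five expectations worded 'if assigned to the Instagram page'. Obtain agreement, the username (or at least willingness to give it) and the baseline survey, and randomise only those who agree. Then send the 10-week survey to every randomised person whether or not they follow the page, analyse them as randomised, and report how many did not follow it. The bias from this step is then zero, because all those randomised have already passed it.

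The cost is a reordering of survey pages and a protocol amendment. Controls may also give a username, a modest privacy burden. Recruitment rises: 80/(1 - 0.10) ≈ 89 or 80/(1 - 0.20) = 100 eligible people must be approached to randomise 80. The results then apply to people willing to use such a page.

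If agreement has to stay after randomisation, the minimum is to take baseline from everyone first and to survey and analyse all refusers as randomised, with refusals reported. This also removes the bias, but it dilutes the effect. If refusers gain nothing, a true .20 becomes .20 × 0.90 = .18 or .20 × 0.80 = .16, and the sample size needed rises by 1/0.90² = 1.23 or 1/0.80² = 1.56.

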In light of these data, the aim of the current study is to test the efficacy of a fully online, Instagram-based intervention designed to reduce heavy alcohol use among young adults. Participants will be randomly assigned to either an intervention or an assessment-only control condition. Analyses will compare mean changes in past-month alcohol use, alcohol-related consequences, mindfulness, and use protective behavioral strategies in intervention versus control group participants at 10-week follow-up. Secondary analyses will assess the perceived acceptability of the intervention and its posts, as well as the degree to which the posts were seen and remembered by participants. It is hypothesized that (1) participants in the intervention group will show greater decreases in alcohol use and consequences and greater increases in mindfulness and protective behavioral strategy use than participants in the control group and (2) intervention posts will be remembered and given high acceptability ratings.

Pilot Work

The proposed project will build on a pilot study conducted by the PI between April 2021 and December 2021. During this pilot study, 50 Wayne State University students between the ages of 18-28, who reported regular binge drinking, were given an Instagram-based alcohol intervention (developed specifically for the study by the PI). After an initial orientation session, participants were asked to follow the study Instagram page and were then shown intervention posts each day for 6 weeks. A subset of participants was also exposed to a series of Instagram ‘stories’

(i.e., images that are available for viewing for twenty-four hours after posting), which were posted once every two days. Instagram content consisted of mindfulness exercises, presentation of drinking norms, information about protective behavioral strategies, and specific affirmations (described in more detail below).

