In order to prevent delays between baseline survey completion and the start of the Instagram intervention, subgroups of participants may be randomized to condition and exposed to the intervention in different data collection waves. Each wave will last for six weeks and will contain a total of forty-two Instagram posts and twenty-one Instagram ‘stories’ (i.e., images that are available for viewing for twenty-four hours after posting and can utilize mechanics like polls and quizzes). Intervention content will be posted once per day throughout the 6-week intervention period, alternating between posting times of approximately 8 AM EST/EDT and 8 PM EST/EDT, and intervention ‘stories’ will be posted once every two days.

10-Week Follow-Up Survey. Ten weeks after the intervention start date (and four weeks after the end of the intervention), participants will be emailed a follow-up survey, which will contain the same questionnaires as the baseline survey. Participants in the intervention condition will also be asked to rate how relevant, respectful, helpful, empathic, personalized, and interesting they felt the intervention content had been, using 5-point Likert scales. Additionally, participants in the intervention group will be shown specific examples of previously posted content and asked to rate each specific post on the dimensions listed above, as well as to indicate whether they remembered seeing those particular posts.

The follow-up survey will remain open for two weeks, and reminder messages will be sent during this time to encourage participant completion. Each participant will receive \$10 for completing the baseline session and \$15 for completing the 10-week online follow-up survey.

Analytic Strategy and Hypotheses

The data will be assessed for normality, missing data, and outliers. Data transformation, multiple imputation, and list-wise deletion will be utilized as needed. Mixed repeated-measure ANOVAs will be used to analyze within- and between-group differences in participants' alcohol consumption, alcohol-related consequences, mindfulness practices, and use of protective behavioral strategies at baseline and 10-week follow-up. Average acceptability ratings will be calculated using group means.

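### Intervention participants answer the self-reported baseline after learning their arm; baseline should be submitted in both arms before allocation is made or disclosed

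*Combined protocol and SAP*

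**What the plan says.** Procedure (Recruitment and Baseline) sets out the intervention arm's steps. After screening, eligible people get access to the main study, and "those randomized to the intervention condition will be invited to follow the study Instagram page". Next comes a consent-like step: "Before being given the Instagram page username, participants will be asked to agree to the following study guidelines/expectations". The first of the five expectations is to follow the intervention page for six weeks. Participants then give their Instagram username and are "sent a baseline survey containing a link to the Instagram page and the baseline questionnaires, and instructed to begin following the Instagram page immediately".

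The same section adds a sentence on waves: "In order to prevent delays between baseline survey completion and the start of the Instagram intervention, subgroups of participants may be randomized" and exposed in different waves.

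For controls, the Participants section describes only a condition "in which they will be emailed assessment measures, but will not be exposed to intervention content". When they complete baseline relative to allocation is not stated.

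The Measures section says "Demographics will be assessed at baseline", and all the efficacy outcomes are questionnaires or a self-completed drinking calendar. The study aim, at the end of the introduction, says "Analyses will compare mean changes in past-month alcohol use, alcohol-related consequences, mindfulness" and protective strategy use between arms at 10 weeks. The Analytic Strategy uses mixed repeated-measures ANOVA on baseline and follow-up, with multiple imputation and list-wise deletion as needed.

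**The concern.** A baseline is a fair reference in a randomised comparison because it is recorded before allocation can influence it. Here the intervention arm has been invited to an alcohol intervention, has agreed to follow it and has been handed the link before answering the first baseline question. Nothing requires the questionnaires to be submitted before the link is opened. If knowing the arm changes how people report past-month drinking, randomisation no longer makes the two baselines comparable, and the resulting difference cannot be told apart from chance imbalance.

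Direction matters for the stated hypothesis of greater decreases in drinking. Over-reporting at baseline by the intervention arm would create apparent benefit. Under-reporting would hide real benefit or suggest harm.

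A second point is inferred rather than stated. The expectations step is described for the intervention arm only and comes before baseline. The plan does not say what happens to someone who declines. Such a person could leave that arm with no baseline outcomes and no demographics, only the screening answers. List-wise deletion would drop them, and imputation would have almost nothing to work from.

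**Working it through.** **Order of events.** For the intervention arm the text gives: screening, randomisation, invitation, expectations, username, then one survey holding link and questionnaires. The invitation and the expectations each reveal the arm, so moving the link to the end of the survey would not be enough. The wave sentence implies that baseline is completed before content starts. It does not place baseline before randomisation or disclosure.

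**Inputs for the illustration.** From the plan: 40 per arm, and a change-by-group comparison. Assumed, because the documents give no value: two-sided 5% test, outcome SD of 1 at both times, pre-post correlation *r* of 0.3 to 0.7, no dropout, no true effect, baseline shift *s* of 0.10 to 0.20 SD in the intervention arm and none in controls.

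**Standard error of the difference in change.** SE = √[2(1 − *r*) × 2/40]:
- *r* = 0.3: √0.070 = 0.265
- *r* = 0.5: √0.050 = 0.224
- *r* = 0.7: √0.030 = 0.173

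**Rejection rate with no true effect.** Noncentral *t*, 78 degrees of freedom, critical value 1.991, noncentrality = bias/SE. For example, 0.20/0.224 = 0.89.

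| Bias (SD) | *r* = 0.3 | *r* = 0.5 | *r* = 0.7 |
|---|---|---|---|
| 0.10 | 6.6% | 7.3% | 8.8% |
| 0.20 | 11.6% | 14.3% | 20.7% |

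At *r* = 0.5 the rejections fall almost entirely on the side of the bias: 6.4% against 0.8% at 0.10 SD, and 14.1% against 0.2% at 0.20 SD, where an unbiased test has 2.5% on each side. If baseline drinking is under-reported, the larger figure is false harm; if over-reported, it is false benefit.

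**Persistence to follow-up.** Let *k* be the share of the shift still present at 10 weeks. The current order gives absolute bias (1 − *k*)*s*; baseline before allocation gives *ks*. At *s* = 0.20:

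| *k* | Current order (SD) | Baseline first (SD) |
|---|---|---|
| 0 | 0.20 | 0 |
| 0.5 | 0.10 | 0.10 |
| 1 | 0 | 0.20 |

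Under the current order at *r* = 0.5, with half the shift persisting, total rejection is 5.6% to 7.3% for *s* of 0.10 to 0.20; with all of it persisting, it is 5%.

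**Loss of decliners.** Suppose *d* of 40 decline and their change would have been 0.5 SD worse than that of those who stay (both assumed). Leaving them out moves the intervention mean by *d* × 0.5/40 in its favour: 0.025 SD for *d* = 2, 0.05 for *d* = 4 and 0.10 for *d* = 8.

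**The case against.** The strongest objection is that the fix need not reduce total bias. Participants still know their arm at 10 weeks, and in that same survey "Participants in the intervention condition will also be asked to rate how relevant, respectful, helpful" and so on. If more than half of any reporting shift persists, the current order cancels more of it than a clean baseline would. That is correct, and the persistence table shows it. But cancellation needs similar shifts at both times, which nobody can verify, whereas a pre-allocation baseline is comparable by design.

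Other points stand as limits:
- The calculation gives controls no shift. Their timing is undocumented; if they also know their arm at baseline, the net difference could be smaller or larger.
- The error rates are not an upper bound. Shifts of opposite sign at baseline and follow-up would add together.
- The number of decliners and their outcomes are invented for illustration. Re-ordering does not stop people declining; it ensures they have a baseline, and they must then be followed up and analysed.
- Screening already records binge frequency before allocation, which may restrain later answers on that outcome but does not cover the others.

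The wave sentence could be read as baseline first and randomisation second. That reading conflicts with the more specific step-by-step account, so the text needs correcting either way.

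**Conclusion.** The concern holds and should be fixed. Followed as written, the procedure gives an allocation-aware baseline in the intervention arm, and that baseline is the reference for every efficacy comparison. The sequence is documented; the size and direction of any bias are not. Rejection of 7.3% to 14.3% instead of 5% illustrates what shifts of 0.10 to 0.20 SD would do at a correlation of 0.5, if confined to the intervention arm and gone by 10 weeks. It is not an estimate for this trial. Arm-specific loss before baseline is a reasonable inference, not a stated feature. The case for change is an uncontaminated baseline on everyone randomised at almost no cost, not a promise of lower total bias in every scenario.

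**What to change.** Rewrite Recruitment and Baseline so that:
1. All eligible participants, in both arms, complete and submit the baseline questionnaires and demographics before randomisation is carried out or disclosed.
2. Randomisation follows, within the wave if waves are used. The intervention arm then receives the expectations, username request and page link in a separate message.
3. The control arm's sequence is stated, and the wave sentence is aligned with this order.
4. Anyone who declines the page is still sent the 10-week survey, and everyone randomised is analysed in the assigned arm.
5. Self-report bias at 10 weeks is acknowledged as a remaining limitation of the unblinded design.

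The cost is re-sequencing an online survey and sending one further message. No extra participants or measures are needed.

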Past Month Alcohol Use will be assessed with The Timeline Follow-Back (TLFB; Sobell & Sobell, 1996), a highly reliable interview that uses a calendar and multiple procedures to aid in the retrospective reporting of substance use. During the TLFB, participants are asked to report how many standard drinks they consumed each day, during the past 30 days. Before beginning the task, participants will be provided with a graphic that illustrates the size of a standard drink (Figure 1), as well as a calendar marked with major holidays (Figure 2). The online version of the TLFB has been found to be a reliable measure of alcohol use in young adult samples (Rueger et al., 2012).

Past-Month Alcohol Consequences will be assessed using the Brief Young Adult Alcohol Consequences Questionnaire (BYAACQ; Kahler et al., 2005), a well-validated 24-item questionnaire designed to assess high- and low-level drinking consequences commonly experienced by young adults. The BYAACQ has shown good validity among young adults and is

designed to be sensitive enough to detect drinking consequences within non-clinical samples (Stamates, Yang, & Lau-Barraco, 2022).

Protective Drinking Practices will be assessed with the Protective Drinking Practices Scale (PBS; Martin et al., 2020), a 20-item questionnaire which measures the frequency of protective behavioral strategy use in the past month (e.g., “Limited cash before going out” rated on a Likert scale ranging from ‘Never’ to ‘Always’). This measure has shown good validity for use among young adults in the United States (Jordan et al., 2021).

Mindfulness Practices will be assessed using the Mindful Attention Awareness Scale (MAAS; Brown & Ryan, 2003). The MAAS is a 15-item questionnaire that assesses the frequency of engaging in mindfulness and mindfulness-related practices (e.g., “I find it difficult to stay focused on what’s happening in the present” rated on a Likert scale ranging from ‘Almost Always’ to ‘Almost Never’). The MAAS has been well-validated in young adult populations (MacKillop & Anderson, 2007).

Intervention Acceptability will be assessed using six domains of acceptability (i.e., relevant, respectful, helpful, empathic, personalized, and interesting). A selection of individual posts will be rated, in addition to the overall intervention. Ratings will be made using single-item, 5-point Likert scales.

Intervention Content

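### If participants are randomised in waves, no balance of arms within wave is stated and the group-by-time ANOVAs have no wave term: a small, avoidable loss of precision, not a bias

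*Combined protocol and SAP*

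**What the plan says.** Under Procedure (Recruitment and Baseline), the plan allows that "subgroups of participants may be randomized to condition and exposed to the intervention in different data collection waves", to avoid a delay between the baseline survey and the start of the intervention. It adds that "Each wave will last for six weeks". The number and size of the waves are not given, and waves are an option rather than a commitment.

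The only allocation figure is in the Participants section: "with an N of 80 (two groups of 40", an overall total. No section states an allocation ratio, blocking or stratification within wave.

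Under Analytic Strategy and Hypotheses, "Mixed repeated-measure ANOVAs will be used to analyze within- and between-group differences" in consumption, consequences, mindfulness and protective strategies at baseline and 10 weeks. The factors implied are group and time; wave is not mentioned.

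The drinking outcome (Measures, Past Month Alcohol Use) asks "how many standard drinks they consumed each day, during the past 30 days", with the aid of a calendar on which major holidays are marked.

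**The concern.** With two time points, the group × time test compares mean change between arms. A stable difference in drinking level between waves cancels out of a change score. A difference in change between waves does not, and it is plausible here: each wave has its own baseline and follow-up recall windows, and drinking can vary with the calendar. If wave is left out of the model, that variation stays in the error term. If the arms are also not balanced within each wave, a chance uneven split moves the estimate a little.

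At stake is precision in a trial of 80 people. Usual practice is to analyse by the groups within which the trial randomises, and to name that factor before the data are seen.

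**Working it through.** **The plan's own figure.** The plan has no figure on waves to reproduce. Its power statement (80 people, effect size .20) gives no metric, alpha or power level. That is a separate matter, but it means the effect size below has to be assumed.

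**Inputs**
- From the documents: n = 80, 40 per arm; two time points; group and time as the only factors.
- Assumed: two-sided 5% test; complete data; 2 or 4 equal waves; the same allocation ratio in every wave; change-score variance scaled to 1, of which a share p lies between waves (p = 0 to 0.10); effect 0.63 SD of change, which 40 per arm detects with about 80% power; and 0.20 SD as an alternative.

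**What p means.** Two equal waves whose mean changes differ by D contribute variance D²/4, so D = 2√p. This gives D = 0.20 SD at p = 0.01, 0.45 SD at 0.05 and 0.63 SD at 0.10. The top value is as large as the assumed treatment effect.

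**Power.** With neither step the standard error is √(4/80) = 0.224 on 78 df. With blocking and the wave term (W waves) it is √(4(1 − p)/80) on 79 − W df. Power comes from the noncentral t distribution with noncentrality effect/SE. For example, at 0.63 SD it is 0.63/0.2236 = 2.82 with neither step, and 0.63/√(4 × 0.90/80) = 2.97 with both at p = 0.10.

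| Wave share p | Gap, two waves | Both steps, 0.63 SD (neither: 79.5%) | Both steps, 0.20 SD (neither: 14.3%) |
|---|---|---|---|
| 0 | 0 | 79.4–79.5% | 14.3% |
| 0.01 | 0.20 SD | 79.8% | 14.4% |
| 0.05 | 0.45 SD | 81.4% | 14.8% |
| 0.10 | 0.63 SD | 83.5% (83.4% with four waves) | 15.4% |

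At p = 0 the exact values are 79.46% with neither step, 79.45% with two waves and 79.42% with four, so the worst loss is about 0.04 points. The gain at 0.05 and 0.10 is what about 80/0.95 − 80 = 4 or 80/0.90 − 80 = 9 extra participants would add.

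**Type I error, arms balanced within wave but wave omitted.** The ratio of reported to true standard error is √{[78(1 − p) + 80p] / [78(1 − p)]} = 1.027 at p = 0.05 and 1.055 at p = 0.10. The actual error rates are then 4.4% and 3.9%, slightly conservative. Simulation (60,000 runs per setting) gave 3.8–4.5%, with power of 79.9–80.8% without wave against 81.3–83.5% with it.

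**Type I error, arms not balanced within wave and wave omitted.** Simulation with a 40:40 split overall gave 5.0–5.1%.

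**Chance imbalance.** Suppose two waves of 40 are filled from one 40:40 list. The number of intervention participants in the first wave then has an SD of 2.25 (hypergeometric). The resulting shift in the estimate has an SD of D × 2 × 2.25/40, that is 0.050 at p = 0.05 and 0.071 at p = 0.10. The standard error of 0.224 already covers it.

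**The case against.** The strongest reply is that nothing in the plan is wrong. Each subgroup is itself randomised to condition, so controls are concurrent, share their wave's calendar windows and protect the comparison. The test keeps its error rate. Waves may not be used at all, and if they do not differ the fix gains nothing. A 5–10% share also means that two waves differ by 0.45–0.63 SD in mean change, which the documents give no ground to expect; at a 0.20 SD gap the gain is about 0.4 points. All of this stands, and it sets the size of the point. It does not remove the case for a step that costs almost nothing and has to be settled before randomisation.

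Three stronger readings are tempting, and the documents support none of them.

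- A reader might infer that omitting wave biases the result or inflates type I error. Concurrent randomisation and the figures above say otherwise.
- A reader might infer that holidays falling in only one wave's recall window distort the comparison. The plan does not say that waves run one after another, and within a wave both arms share the same windows.
- A reader might infer that the shared page makes the standard errors wrong. Intervention participants do use a common page where, of their comments, "other participants will be able to view them and interact with them". But commenting is voluntary, contacting other participants is listed as trolling, and no correlation is given from which an error rate could be derived. This is a separate matter that exists with or without waves, a wave term would not address it, and it adds nothing to the present point.

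**Conclusion.** The point holds in a limited form. If more than one wave is run, the plan states no balance of arms within wave and specifies no wave term, which gives up some precision and allows avoidable chance imbalance. The planned test remains valid.

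The gain from changing it runs from nil (no wave variance) through about 0.4 points (1% share) to 2 to 4 points (5–10% share) at an assumed effect of 0.63 SD, and is at most about 1 point at 0.20 SD. Wave share, number of waves, effect size, alpha and complete data are all assumptions. Severity is low.

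**What to change.** If waves are used, randomise 1:1 in blocks within each wave, and name wave and wave × time as terms in every outcome ANOVA before data collection starts. The two steps belong together: blocking without the wave term leaves the reported standard error slightly too large. A group × wave × time term is not needed for the main test.

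The cost is a blocked list per wave and one degree of freedom for two waves, up to three for four. If waves turn out not to differ, the loss is below 0.1 power points. No extra participants or data are needed.

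As a separate and optional addition, one sentence in the limitations could note that intervention participants share an interactive page, so their outcomes may be correlated.
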